8. STATISTICAL ANALYSIS

If the protocol you are submitting has a statistical plan within it, please confirm here, by checking the box

If the protocol does not contain a statistical plan, please address these points:

- Describe how your data will be used to test the hypotheses.
- State clearly what variables will be tested and what statistical tests will be used.
- Include sample size calculations.
- If this is a pilot study, state which variables will be examined for hypothesis generation in later studies.

Descriptive statistics, including frequencies, proportions, means, standard deviations, medians, and interquartile ranges, will be used to describe the study sample.

The aim of this study is to determine the sensitivity and specificity of synthesized 18-lead ECG in the diagnosis of posterior-lateral and/or right-ventricular ischemia, using actual 18-lead ECG as the gold standard. Accuracy, positive predictive value, and negative predictive value will also be calculated. A 2x2 table will be created as shown below:

		Actual 18-lead ECG (Gold Standard)		
		Positive	Negative	
Synthesized 18-lead ECG	Positive	A	B	A + B
	Negative	C	D	C + D
		A + C	B + D	Total

Sensitivity will be calculated by using this formula: $A / (A + C)$

Specificity will be calculated by using this formula: $D / (B + D)$

Accuracy will be calculated by using this formula: $(A + D) / (A + B + C + D)$

Positive predictive value will be calculated by using this formula:

$$[(\text{Sensitivity})(P)] / [(\text{Sensitivity})(P) + (1 - \text{Specificity})(1 - P)]$$

Where P = prevalence of outcome

Negative predictive value will be calculated by using this formula:

$$[(\text{Specificity})(1-P)] / [(\text{Specificity})(1 - P) + (1 - \text{Sensitivity})(P)]$$

Where P = prevalence of outcome

Based on a review of data from the North Shore University Hospital's Emergency Department, the prevalence of our outcome is estimated to be 10%. Our study will

enroll 300 patients; therefore, we estimate that 30 of these patients will have our outcome of interest and 270 will not. Based on a previous study by Tamura et al. published in the American Journal of Cardiology in 2014, sensitivity is estimated to be 83% and specificity is estimated to be 99%. Therefore, among the 30 patients with our outcome, the proportion of test positive by the synthesized 18-lead ECGs is estimated to be 83% with a corresponding 95% CI of 65% to 94%. Among the 270 patients without our outcome, the proportion of test negative by the synthesized 18-lead ECG is estimated to be 99% with a corresponding 95% CI of 97% to 100%.

No formal sample size calculations were performed for this study. Data collected from this study will allow us to perform a formal sample size calculation for future studies.

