2. BRIEF SUMMARY OF RESEARCH

- *The summary should be written in language intelligible to a moderately educated, non-scientific layperson.*
- *It should contain a clear statement of the rationale and hypothesis of your study, a concise description of the methodology, with an emphasis on what will happen to the subjects, and a discussion of the results.*
- *This section should be no more than ½ page*

This study, sponsored by Nihon Kohden, aims to determine the sensitivity and specificity of synthesized 18-lead electrocardiogram (ECG) in the diagnosis of posterior-lateral and/or right-ventricular ischemia, using actual 18-lead ECG as the gold standard. The synthesized 18-lead ECG calculates six extra leads of information from the standard 12-lead ECG done in the Emergency Department (ED). Nihon Kohden has created synECi18 Technology, which can mathematically synthesize and display the extra leads.

A standard 12-lead ECG records electrical information primarily from the left side of the heart, both anterior and inferior. A 12-lead ECG is commonly performed in the ED to detect abnormal heart rhythms and is the standard of care for patients with chest pain or suspected cardiac ischemic conditions. An 18-lead ECG records the same information as the 12-lead ECG, in addition to six leads that record the electrical information from the right and posterior sides of the heart. 12-lead ECGs are generally considered poor at recording electrical information from the right and posterior sides of the heart.

The patient population (n=300) will consist of patients who present to the North Shore University Hospital or Long Island Jewish Medical Center ED with a chief complaint of chest pain, chest pressure, or chest discomfort. These patients will be receiving a standard 12-lead ECG as part of their routine clinical care. Patients with ST-Elevation Myocardial Infarction (STEMI) will be excluded from the study as they need to be immediately sent to the cardiac catheterization lab and approaching these patients for informed consent to participate in this study would interfere with patient care. Additionally, patients with a known positive troponin value will also be excluded as they also require immediate clinical care.

Trained ED study technicians will use ECG machines provided by Nihon Kohden to obtain two consecutive 15-lead ECGs. The 15-lead ECG consists of a traditional 12-lead ECG and an additional three leads on the right side of the body. The first 15-

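### Does leaving P undefined in the PPV and NPV formulas make the predictive values ambiguous?

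*Combined protocol and SAP*

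**What the plan says.** Section 8 sets out a 2x2 table of synthesized against actual 18-lead reads, with cells A to D and their margins, and takes the actual read as the reference. Sensitivity, specificity and accuracy are written directly in the cells. The two predictive values are introduced by "Positive predictive value will be calculated by using this formula" and "Negative predictive value will be calculated by using this formula". Each formula that follows is the Bayes form in sensitivity, specificity and P, with the note "Where P = prevalence of outcome" and nothing more.

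A new paragraph then turns to planning. From a review of data at the North Shore ED, it says "the prevalence of our outcome is estimated to be 10" percent. It goes on: "we estimate that 30 of these patients will have our outcome of interest and 270 will not". The same paragraph takes 83% sensitivity and 99% specificity from an earlier published study and gives the confidence intervals expected at those values. It states no PPV or NPV, and no sentence links the 10% to P.

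**The concern.** P is the one input to Section 8's formulas that is not tied to the 2x2 table, and the only prevalence in the documents appears directly after the formulas. One analyst could insert the observed proportion of reference positives and another the 10%. They would report different predictive values from the same data, and the choice could be made after the table was seen.

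There are also reasons why the study proportion might not be 10%. The figure comes from one ED, while Section 2 describes "patients who present to the North Shore University Hospital or Long Island Jewish Medical Center ED". STEMI patients are excluded, and "patients with a known positive troponin value will also be excluded". Section 3 describes a convenience sample. Section 2 says that a 12-lead ECG "is the standard of care for patients with chest pain or suspected cardiac ischemic conditions", and Section 8 does not say how the outcome was established in the data review. If fewer than 10% of patients were positive on the actual read, using P = 10% would give a PPV above the one observed in the sample and an NPV slightly below it. Above 10% the directions reverse.

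**Working it through.** **Inputs.** From Section 8: n = 300, prevalence 10%, sensitivity (Se) 83%, specificity (Sp) 99%, and the PPV and NPV formulas. Assumed: every count of reference positives other than 30. Cells are rounded to whole patients.

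**1. The plan's own figures.** 300 × 0.10 = 30 positives, leaving 270 negatives. Rounding gives 25 of 30 and 267 of 270. Exact 95% intervals are 65.3% to 94.4% and 96.8% to 99.8%, which match the stated 65% to 94% and 97% to 100%. There is no PPV or NPV figure to reproduce.

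**2. What the formulas give when P = (A+C)/Total.** Write N for Total.

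- Se × P = A/(A+C) × (A+C)/N = A/N
- (1 − Sp)(1 − P) = B/(B+D) × (B+D)/N = B/N
- PPV = (A/N) / (A/N + B/N) = A/(A+B)
- By the same steps, NPV = D/(C+D)

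**3. At the planned split** (A, B, C, D = 25, 3, 5, 267): PPV = 25/28 = 89.3% and NPV = 267/272 = 98.2%. P = 10% gives the same values, because the sample prevalence is also 10%.

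**4. If P = 10% is used whatever the sample shows.** Worked case with 20 positives (17, 3, 3, 277): Se = 17/20 = 0.85 and 1 − Sp = 3/280 = 0.0107. PPV at 10% = 0.085/(0.085 + 0.0107 × 0.9) = 0.898, against 17/20 = 0.850 from the table.

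| Positives of 300 | A, B, C, D | PPV from table | PPV at P = 10% | Gap (points) | NPV from table | NPV at P = 10% |
|---|---|---|---|---|---|---|
| 9 (3%) | 7, 3, 2, 288 | 70.0% | 89.3% | +19.3 | 99.3% | 97.6% |
| 15 (5%) | 12, 3, 3, 282 | 80.0% | 89.4% | +9.4 | 98.9% | 97.8% |
| 20 | 17, 3, 3, 277 | 85.0% | 89.8% | +4.8 | 98.9% | 98.3% |
| 30 (10%) | 25, 3, 5, 267 | 89.3% | 89.3% | 0 | 98.2% | 98.2% |
| 41 | 34, 3, 7, 256 | 91.9% | 88.8% | −3.1 | 97.3% | 98.1% |
| 45 (15%) | 37, 3, 8, 252 | 92.5% | 88.6% | −3.9 | 96.9% | 98.0% |

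The counts 20 and 41 are the 2.5th and 97.5th percentiles of a binomial with n = 300 and probability 0.10, so they bound what the plan's own assumption makes likely. The rows at 3%, 5% and 15% lie outside that range.

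**5. Against sampling error.** The exact 95% interval for 25/28 is 71.8% to 97.7%, about 26 points wide. For 7/10 it is 34.8% to 93.3%, which still contains the 89.3% obtained with P = 10%.

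**6. Which reading the text supports.** Section 8 announces accuracy and the two predictive values together and then says that a 2x2 table will be built. The sensitivity and specificity inside the PPV and NPV formulas are the cell-based quantities defined just above them, and the table prints the margins that give P. The 10% belongs to the paragraph that also carries 83% and 99%. No analyst would put those planning values into the PPV formula in place of the observed ones, and the 10% has the same standing.

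**The case for a change.** The best case for a change starts from the choice of formula. If P were simply the sample proportion, A/(A+B) and D/(C+D) would have been shorter, and both denominators are already margins of the printed table. Using the prevalence form, just before a prevalence figure, invites the reader to put that figure in. The resulting difference is systematic, so a wide confidence interval does not excuse it. The remedy would cost only a sentence or two.

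Part of this stands. The text does not define P, the two readings do diverge, and a low sample prevalence cannot be ruled out from the documents. The inference that 10% was intended does not stand. It rests on adjacency alone, and the Bayes form is algebraically equivalent to the cell form when P comes from the table. Anyone holding the four cells can compute A/(A+B) and D/(C+D) directly, so the sample values cannot be lost. Predictive values computed at a stated external prevalence are also a legitimate quantity, and the only fault would be failing to label them as such. How the outcome was established in the ED review bears on the 30/270 planning split. It reaches PPV and NPV only if P is set to 10%.

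**Conclusion.** The concern is accurate about the wording but does not call for a change. P is an unspecified input to two correct formulas, and an analyst working from the 2x2 table will take it from that table. Were 10% used instead, the PPV discrepancy would be about +4.8 to −3.1 points over 20 to 41 positives, and NPV would differ by less than 1 point. This assumes a true prevalence of 10% and the plan's 83% and 99%. Gaps of 9 to 19 points need a sample prevalence of 3% to 5%, which is an assumption, combined with a reading of P that the text does not favour.

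Predictive values are additional measures here. The stated aim is sensitivity and specificity, which do not involve P, and neither does accuracy. No sample size or decision rule depends on PPV or NPV, and the plan says that no formal sample size calculation was made. Adding confidence intervals for the predictive values, or projections at other prevalences, would be optional extras.

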lead ECG will have an additional three electrodes/stickers on the right side of the chest and the second 15-lead ECG will have an additional three electrodes/stickers on the posterior side. This means the patient will have a total of six extra electrodes/stickers placed on their body—three on the right side of the chest and three on the back. Each ECG takes about 15 seconds to obtain, of which 10 seconds are recorded by the machine. The two 15-lead ECGs are then saved onto the ECG machine identified by a patient ID number and printed.

The saved information will later be input into an algorithm to calculate the synthesized 18-leads. This will occur towards the end of the study, and the patient will not be involved in this process. In other words, the device will take the actual information from the standard 12-leads and synthesize the six extra leads. The actual 18-leads (composed of the two 15-leads conducted in the ED) will be compared with the synthesized 18-leads produced by the synECi18 technology. A study cardiologist will evaluate the actual 18-lead ECGs and synthesized 18-lead ECGs and determine whether there is posterior-lateral and/or right-sided ventricular ischemia. The cardiologist will be blinded to the type of waveform they are analyzing (synthesized versus actual). There will only be one cardiologist who will evaluate ECGs for this study in a blinded fashion. The actual 18-lead ECGs will be used as the reference for comparison. The synthesized 18-lead ECGs will be compared with the actual 18-lead ECGs to calculate sensitivity and specificity.

The study will not interfere with patient care or treatment, however, the two 15-lead ECGs done in the ED will be shown to the physician who can determine whether or not to order an official 18-lead ECG in the hospital's electronic medical record system.

We hypothesize that the synECi18 synthesized 18-lead ECGs will provide high sensitivity and specificity for diagnosing posterior-lateral and/or right-ventricular ischemia, with the actual 18-lead ECGs being used as the reference for comparison.

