5. NUMBER OF SUBJECTS

- *Indicate the total number of subjects to be accrued locally. If applicable, distinguish between the number of subjects who are expected to be pre-screened, enrolled (consent obtained), randomized and complete the research procedures.*

The first phase of the study will be a pilot study, which will consist of enrolling 10 subjects to pilot test our data collection procedures and operations outlined in this protocol, as well as to troubleshoot issues that we did not expect. After our data collection procedures and operations are pilot-tested, the study will move onto the next phase for data collection.

The pilot study phase may take approximately two weeks to enroll 10 subjects. The main phase of the study will be the data collection phase, which is estimated to take 6 months. The data collection phase will consist of enrolling the remaining 290 subjects in the ED at NSUH or LIJMC.

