6. STUDY TIMELINES

- *Describe the duration of an individual's participation in the study*
- *Describe the duration anticipated to enroll all study subjects*
- *The estimated date of study completion*

The study will require obtaining two 15-lead ECGs on all enrolled patients. Each ECG takes approximately 30-seconds to complete. Placing the additional six electrodes/stickers on the patients will take less than five minutes. This means that the study ECG procedures should only take less than approximately 8 minutes. The consent process length will depend on the questions the patient has about the study. As stated, the patient will be left with the consent form for about 10 minutes to read it over in private. Taking into account this time, the consent time, and the study itself, we expect each patient enrollment will take 25 to 30 minutes.

The full study is expected to last approximately 9 months and will consist of three total phases. The first phase will be a pilot study conducted on 10 subjects to pilot test our procedures and operations of data collection outlined in the protocol. After we pilot test our procedures and operations, the study will move onto the data collection phase. This pilot study phase, which requires enrolling 10 subjects, will take approximately two weeks.

The main phase of the data collection period is expected to take about 6 months. This phase requires the enrollment of 290 subjects at NSUH ED and LIJMC ED. It is estimated that target patient enrollment could be 5 subjects per day per hospital, allowing the study to collect 50 patient ECG data sets per week. It is expected that data collection may be complete sooner than 6 months, however, some delays are taken into consideration. The study will begin at NSUH ED and once it is running well there, it will begin at LIJMC ED.

The evaluation phase of the study is expected to take 3 months. This phase will consist of analyzing all of the data.

Table of timeline:

Pilot Study Phase (Month 1)	Main Data Collection Phase (Months 2-6)	Evaluation Phase (Months 7-9)

 • Pilot trial with up to 10 subjects 	
 • Subject enrollment (290 subjects) • Data collection 	
 • ECG analysis • Data report

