- 9) Following the patient's ED visit, an AA will use the MRN and the ECG date from the data entry form to obtain test results for the patient obtained during their ED stay. These include troponin test, CAGs, CTA, stress echos, or nuclear stress tests. This data will be entered directly into the REDCap database (see attachment 2). Only IRB approved study personnel will have access to this database. At the end of the study, NKC, the sponsor, will be provided with the de-identified version of the data sheet (i.e. all points included in attachment 2 except the MRN).
- 10) All ECGs (synthesized and actual) in this study will be assigned a random code by the Academic Associate on this study, [name], and only she will have access to this code. The ECGs will be coded randomly with numbers provided by the randomization tool in Excel. The file with the random codes will be saved onto Northwell Health servers and a password will be placed on that document. Once coded, the ECGs will be put in numerical order to avoid ECGs from the same patient being back to back. The study cardiologist will analyze the ECGs in that numerical order and determine whether or not the ECG shows evidence of ischemia. This coding will shuffle the ECGs from all patients and all dates. The study cardiologist will not know which ECGs are synthesized vs. actual. The study cardiologist will record the random code on the ECG and their interpretation for that ECG on a form (form attached). The form will be provided to the Academic Associate, who will decode the ECG and enter the data into REDCap. Given that there will only be one study cardiologist, there will be no need to evaluate inter-rater reliability.
- 11)

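### Does a fixed enrolment of 300, with ischemia-positive patients counted only afterwards, leave the expected sensitivity interval of 65% to 94% unprotected?

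*Combined protocol and SAP*

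**What the plan says.** Section 8 (Statistical Analysis) defines sensitivity as A/(A + C), where A + C is the number of patients positive on the actual 18-lead ECG. From a review of data at one of the two hospitals it states that "the prevalence of our outcome is estimated to be 10" per cent. It then says the study will "enroll 300 patients; therefore, we estimate that 30 of these patients will have our outcome of interest and 270 will not". With sensitivity taken as 83% and specificity as 99% from a published study, it gives expected 95% intervals of 65% to 94% and 97% to 100%. The section ends with "No formal sample size calculations were performed for this study" and adds that the data will support such a calculation for later studies.

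Enrolment is defined by the total. After 10 pilot patients, section 5 says: "The data collection phase will consist of enrolling the remaining 290 subjects in the ED at NSUH or LIJMC".

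On timing, section 6 puts enrolment in Months 2-6 and ECG analysis in Months 7-9, and says of the evaluation phase: "This phase will consist of analyzing all of the data". Section 2 says of the synthesis: "This will occur towards the end of the study, and the patient will not be involved in this process". Section 7 says of the random codes given to all tracings: "This coding will shuffle the ECGs from all patients and all dates". Section 6 also gives a possible accrual rate, "allowing the study to collect 50 patient ECG data sets per week".

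**The concern.** Three features combine. First, the denominator of sensitivity is the count of positives, which the plan does not control. Second, the 10% comes from one of the two enrolling emergency departments. The documents do not say whether that review left out STEMI patients and patients with a known positive troponin, as this study does. Leaving them out could lower prevalence, although the documents do not establish the direction. Third, the pooled shuffle and the timeline imply that the study learns the number of positives only when enrolment is over. No sentence says so outright, and treating physicians do see the printed tracings at once, but no study count is made from them.

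Sensitivity is half of the study's aim and is hypothesised to be high. A shortfall of positives found in Months 7-9 cannot be repaired by analysis. One found during enrolment perhaps could be, since at 50 per week the 290 main-phase patients would take 290/50 = 5.8 weeks of a window of five to six months.

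**Working it through.** **Inputs.** From section 8: N = 300, prevalence 10%, sensitivity 83%, specificity 99%. Prevalences other than 10% are assumptions, shown as a range.

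**The plan's own figures.** Expected positives are 300 × 0.10 = 30. Since 0.83 × 30 = 24.9, take 25 detected. The exact (Clopper-Pearson) 95% interval for 25/30 is 65.3% to 94.4%, which matches 65% to 94%. For specificity, 267/270 gives 96.8% to 99.8%, which matches 97% to 100%. Both figures are right.

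**Chance variation if 10% is right.** The number of positives is Binomial(300, 0.10), with a 95% range of 20 to 41. P(fewer than 20) = 0.017. With 24 positives, 20/24 gives 63% to 95%, little different from the plan.

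**If prevalence is not 10% (N fixed at 300).** Detected counts must be whole numbers, so where 0.83 × positives is not close to one, both neighbours are shown.

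| Assumed prevalence | Expected positives | Exact 95% interval | P(fewer than 20 positives) |
|---|---|---|---|
| 15% | 45 | 37/45: 68% to 92% | – |
| 10% | 30 | 25/30: 65% to 94% | 2% |
| 7% | 21 | 17/21: 58% to 95%; 18/21: 64% to 97% | 38% |
| 5% | 15 | 12/15: 52% to 96%; 13/15: 60% to 98% | 88% |
| 3% | 9 | 7/9: 40% to 97%; 8/9: 52% to 99.7% | over 99% |

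The loss is real at low prevalence, but the lower limits depend noticeably on rounding. A prevalence above 10% narrows the interval.

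**What a safeguard would buy.** Consider a rule under which, after 150 patients, a second cardiologist reads only the actual ECGs and reports k positives. Enrolment is then set to 30 × 150/k = 4500/k, not below 300 and not above 600. The study cardiologist's reading remains the reference.

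- *Both readers agree perfectly.* P(fewer than 20 positives) is under 0.1%, 0.5% and 4.5% at 10%, 7% and 5% prevalence, with mean enrolment of 342, 447 and 541. At 5%, the mean interval width falls from 41 to 30 points. At 10%, it falls only from 29 to 27 points, for about 42 extra patients on average.
- *The second reader finds 90% of the study reader's positives and wrongly calls 5% of the negatives (an assumption).* At 5% prevalence, the expected k is 150 × (0.05 × 0.90 + 0.95 × 0.05) = 13.9, against a true 7.5. The rule then asks for about 4500/13.9 = 324 patients, which yields about 324 × 0.05 = 16 positives. By simulation, P(fewer than 20) is 67% at 5% prevalence and 25% at 7%.
- *90% detection and 3% false calls.* The corresponding figures are 38% and 12%.

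The documents give no figure for agreement between readers. Section 7 plans no inter-rater assessment because there is a single reader.

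**The case for a change.** The strongest case for a change is that the plan does in effect justify 300 by the interval it quotes, states a hypothesis of high accuracy, and promises data for future sample size work, which itself needs a usable sensitivity estimate. The 10% rests on a review whose population is not described. At an assumed 5%, an observed 80% (12/15) could not exclude 52%. Counting reference positives early would expose no synthesized tracing, so it would not bias sensitivity, and the stated accrual rate suggests room to extend.

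Much of this stands: the total is fixed, no floor is set, the count comes late, and the low-prevalence intervals are wide. Three parts do not carry through. Nothing in the documents shows that 10% is too high; the review comes from the hospital where enrolment starts. High sensitivity is never given a threshold, so no number of positives marks success or failure. And the room to extend is less certain than it looks: section 6 offers five per day per hospital only as a possibility, allows for delays and starts at one site. At 25 per week from one hospital, Months 2-6 (about 21.7 weeks) hold about 544 patients, short of 600.

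**Conclusion.** No change follows. The plan misses no figure that it states. The interval of 65% to 94% is what 30 positives would give, is correctly computed, and is presented as an expectation in a study that declares it made no formal sample size calculation. If the 10% holds, the exposure is small, with about a 2% chance of fewer than 20 positives. If prevalence is well below 10%, which is an assumption the documents neither support nor rule out, the sensitivity interval widens to 40 points or so at 5%.

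That widening would be visible, not hidden. The 2×2 table in section 8 shows A + C, and an analyst would naturally report an exact interval on the positives actually observed. An estimate from 15 to 25 positives, with its interval, can still inform a later sample size calculation, which is the use section 8 names.

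Protecting the width means up to 300 more patients, a second cardiologist and a higher approved ceiling. The gain approaches its best-case size only if the two readers nearly always agree. Accepting the risk with a fixed 300 is a fair trade-off. The unstated population behind the 10% is a missing detail that alters neither the design nor the analysis.
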